9.6.4 Vital Signs

Vital signs including systolic/diastolic blood pressure, pulse, respiratory rate, and temperature will be summarized by changes from baseline values for each treatment group using descriptive statistics.

For the summary of changes from baseline by visit, subjects without a baseline and/or post baseline value will be excluded; values from unscheduled assessments will be excluded. **Subjects with missing data for a scheduled assessment time point will be excluded from the graphical summary for that time point.** Vital sign results taken > 30 days after the last administration of protocol therapy will be excluded from all vital sign summaries.

9.6.5 Electrocardiogram

The electrocardiogram (ECG) measurements from this clinical study were performed as per standard of care for routine safety monitoring, rather than for purposes of assessment of potential QT interval corrected (QTc) effect. Summaries over time and/or changes from baseline over time will be provided by treatment group for all ECG parameters (PR, QRS, QT, QTc, and heart rate).

9.6.6 Antibody Formation

Serum from venous blood samples collected from all subjects in the KdD arm will be assessed for the generation of antibodies to daratumumab (immunogenicity) on day 1 of cycles 1, 7, and 12; as well as both follow-up visits. The number of subjects who test positive for anti-drug antibody will be summarized for each visit. Antibody titers and neutralizing antibodies measurements will be summarized descriptively by visit for these subjects.

9.6.7 Exposure to Investigational Product

Drug exposure (for carfilzomib, dexamethasone, daratumumab, respectively) including duration and intensity will be summarized descriptively for each treatment group.

Descriptive statistics will be produced to describe the exposure to investigational product by treatment group. The number of cycles of protocol-specified therapy administered will be summarized with an additional breakdown of the number of cycles started. In addition, the duration of therapy, the cumulative dose, and the average dose per administration and relative dose intensity will be summarized for each drug. The number and percent of subjects with dose modifications (eg, dose reductions, dose interruptions) and reason for modification will be summarized for both treatment groups.

9.6.8 Exposure to Concomitant Medication

The number and proportion of subjects receiving therapies of interest will be summarized by preferred term for each treatment group as coded by the World Health Organization Drug (WHO DRUG) dictionary. In addition, the number and proportion of subjects receiving anti-myeloma therapies **while on study** will be summarized by WHODRUG preferred term for each treatment group in the Full Analysis Set.

9.7 Other Analyses

9.7.1 Analyses of Pharmacokinetic or Pharmacokinetic/Pharmacodynamic Endpoints

PK samples will be obtained from all subjects to assess the serum concentration of carfilzomib and from all subjects in the KdD arm to assess the serum concentration of daratumumab. Data will be utilized to perform exploratory population PK modeling, but results will not be included in the clinical study report. Details regarding objectives, data handling, and methodology pertaining to any modeling activities will be provided in a separate population modeling analysis plan.

9.7.2 Analyses of Clinical Outcome Assessments

Detailed analyses of clinical outcome assessments are described in the separated Supplemental Statistical Analysis Plan (SSAP) for GHS.

9.7.3 Analyses of Biomarker Endpoints

Pharmacogenomics markers and potential cardiac risk single nucleotide polymorphisms (SNPs) will be explored.

9.7.4 Echocardiogram

Echocardiogram, including LVEF, RVEF, RV Functions and abnormal findings, will be summarized by visit using descriptive statistics for each treatment group based on the Safety Analysis Set. In particular, LVEF, RVEF and RV Functions will also be summarized by actual values and changes from baseline values for each treatment. Additionally, the unscheduled ECHO assessments (as clinically indicated, such as cardiac failure) will be summarized for each treatment group using descriptive statistics, based on the number of adverse events that trigger the unscheduled ECHO assessments.

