7.3.9 Echocardiogram

All subjects will have a baseline transthoracic ECHO (TTE) during screening, including assessments of systolic and diastolic left ventricular function and right ventricular function. Screening ECHO may be done within 30 days prior to randomization, if performed as a part of standard of care. Echocardiograms are to be repeated approximately every 6 months (\pm 2 weeks) from cycle 1 day 1, until end of treatment, or if clinically indicated. Routine ECHO (every 6 months) should not be assessed within 4 days after daratumumab infusion. However, ECHO should be performed within 72 hours of cardiac failure event initiation, regardless of the timing in relation to infusion.

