10.1.1.2 Secondary Endpoint(s)

Key secondary endpoints include:

[figure not shown]
- ORR: defined as the proportion of best overall response of sCR, CR, VGPR, and PR by IRC
- MRD[-]CR rate, MRD[-]CR defined as achievement of CR by IRC per IMWG-URC (see [Appendix M](#)) and MRD[-] status as assessed by NGS (at a 10^{-5} level, pending analytical validation) at 12 months
- OS

Additional secondary endpoints:

- DOR
- time to next treatment
- TTP
- time to response
- sustained MRD[-]CR (defined as the proportion of subjects that maintain MRD[-]CR for 12 months or more after achieving MRD[-]CR status)
- CRR (defined as the proportion of best overall response of sCR or CR)

- MRD [-] rate
- EORTC QLQ-C30- Global Health Status/QoL scale
- subject incidence of treatment-emergent adverse events
- safety laboratory values, LVEF, FEV1/FVC ratio, and vital signs at each scheduled assessment

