10.4.4 Safety Endpoints

The analysis of safety endpoints will be based on the safety analysis set. The number and percentage of subjects experiencing at least 1 adverse event will be summarized by treatment group, relationship of adverse event to study treatment, and severity. Subject incidence of all treatment-emergent adverse events will be tabulated by system organ class and preferred term. Laboratory parameters will be summarized using descriptive statistics, by postdose shifts relative to baseline, and a summary of subject incidence of clinically significant values. Vital signs will be summarized by changes from baseline values for each treatment group using descriptive statistics. The LVEF and FEV1/FVC endpoints will be summarized by changes from baseline values for each treatment group using descriptive statistics. Drug exposure including duration and intensity will be summarized descriptively for each treatment group.

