
time to response (TTR)persistence of MRD[-]CRcomplete response rate (CRR)MRD[-] ratequality of life	
TTNT, defined as the time from randomization to the initiation of subsequent non-protocol anti-cancer treatment for multiple myelomaTTP, defined as the time from randomization to documented disease progressionTTR, defined as the time from randomization to the earliest date a response of PR or better is first achieved and subsequently confirmed for subjects with a best response of PR or bettersustained MRD[-]CR, defined as the proportion of subjects who maintain MRD[-]CR for 12 months or more after achieving MRD[-]CR statusCRR, defined as the proportion of subjects with BOR of sCR or CRMRD[-] rate, defined as the proportion of subjects with MRD[-] status as assessed by NGS (at a 10⁻⁵ level) at 12 monthsGlobal Health Status/Quality of Life (GHS/QoL) measured by European Organisation for Research and Treatment of Cancer (EORTC) QLQ-C30 version 3 questionnairesubject incidence of treatment-emergent adverse events (TEAE)safety laboratory values, left ventricular ejection fraction (LVEF), forced expiratory volume in 1 second (FEV1)/forced vital capacity (FVC) ratio, and vital signs at each scheduled assessment

Objectives	Endpoints
Exploratory	
CCI 	

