9.6.2 Adverse Events

The Medical Dictionary for Regulatory Activities (MedDRA) version 20.0 or later will be used to code all events categorized as adverse events to a system organ class and a preferred term.

The subject incidence of adverse events will be summarized for all treatment-emergent adverse events, grade 3 or higher TEAEs, serious adverse events, adverse events leading to withdrawal of investigational product, and fatal adverse events, and adverse events of interest (EOI). In the event that a subject experiences repeated episodes of the same AE, the subject will be counted once within each system organ class and similarly

counted once within each preferred term and the event with the highest severity grade and/or strongest causal relationship to each treatment will be used for purposes of incidence tabulations.

Subject incidence of all treatment-emergent adverse events, grade 3 or higher TEAEs, serious adverse events, adverse events leading to withdrawal of investigational product, and fatal adverse events will be tabulated by system organ class **in alphabetical order** and preferred term in **descending frequency order**.

Subject incidence of events of interest (standardized MedDRA queries and/or Amgen customized queries) will also be summarized according to their categories and preferred term in descending order of frequency. Time to onset and duration of select EOs may also be summarized.

In addition, summaries of treatment-emergent AEs, grade 3 or higher TEAEs, serious adverse events, adverse events leading to withdrawal of investigational product, and fatal adverse events by preferred term in any treatment arm will be provided in descending order of frequency.

Summaries of treatment-emergent and serious adverse events will be tabulated by system organ class, preferred term, and grade. The fatal adverse events **will also be provided** by system organ class **in alphabetical order** and preferred term in descending order of frequency.

A summary of the number of deaths and the cause of death, classified by deaths within 30 days of last dose of study drug and deaths more than 30 days after the last dose, will be provided.

All AEs, including TEAEs, will be included in individual subject listings.

All on study deaths will be listed.

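### SAP 9.7.4 counts unscheduled echocardiograms by triggering adverse event and does not commit to reporting the LVEF values, or the number of subjects affected, at those echocardiograms

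*SAP*

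**What the plan says.** SAP 9.7.4 covers LVEF, right ventricular measures and abnormal findings. These "will be summarized by visit using descriptive statistics for each treatment group based on the Safety Analysis Set", with LVEF also given as actual values and changes from baseline. Unscheduled ECHOs "will be summarized for each treatment group using descriptive statistics, based on the number of adverse events that trigger the unscheduled ECHO assessments".

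The secondary safety endpoint is "safety laboratory values, LVEF, FEV1/FVC ratio, and vital signs at each scheduled assessment" (Protocol 10.1.1.2; SAP 2.1 is equivalent). Protocol 10.4.4 asks only for description: "The LVEF and FEV1/FVC endpoints will be summarized by changes from baseline values for each treatment group using descriptive statistics".

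Under Protocol 7.3.9, ECHOs are repeated about every 6 months "from cycle 1 day 1, until end of treatment, or if clinically indicated". In addition, an "ECHO should be performed within 72 hours of cardiac failure event initiation". The ECHO row of Protocol Table 11 has no entry at the follow-up visit, and the visit list in Protocol 7.2.4 has none either.

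Clinical cardiac events are covered separately in SAP 9.6.2: "Summaries of treatment-emergent and serious adverse events will be tabulated by system organ class, preferred term, and grade".

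**The concern.** The ECHO most likely to show the lowest LVEF is the one prompted by a cardiac failure event, and for that ECHO the SAP names only an event count. An event count says neither how far LVEF fell nor how many subjects were involved, since one subject with three events counts three times.

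The by-visit tables need not fill the gap. For heart failure, Protocol Table 4 holds carfilzomib until resolution and stops it if there is none after 4 weeks. A fall may thus recover before the next 6-monthly ECHO, or it may end treatment and with it the schedule. The second route can differ by arm. Under Protocol 6.2.1.2 a subject remains on protocol treatment while receiving either carfilzomib or daratumumab, so a KdD subject who stops carfilzomib can stay on the ECHO schedule while a Kd subject cannot.

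Cardiac failure is a stated carfilzomib risk that shaped how daratumumab is infused (Protocol 2.5.3). At stake is how well the report describes that risk.

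**Working it through.** There is no plan figure to reproduce. The check traces what is committed to, illustrates the size, and then tests the obvious remedy.

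**1. What is committed to**

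- LVEF at scheduled visits: actual value and change, by visit.
- Unscheduled ECHOs: descriptive statistics based on a count of triggering events. No LVEF value and no subject count is named.
- Worst post-baseline LVEF, maximum fall per subject, or subjects below a threshold: in neither document.
- By contrast, SAP 9.6.3 plans the maximum on-treatment shift for selected laboratory parameters and includes unscheduled values in laboratory change summaries.

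**2. How much a 6-monthly schedule can miss (inputs assumed)**

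A fall lasting w months at a random time meets a 6-monthly ECHO with probability w/6.

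- w = 1: 1/6 = 17%. w = 3: 3/6 = 50%.
- If 5% of 300 KdD subjects (15) have such a fall, 15 × 1/6 = 2.5 to 15 × 3/6 = 7.5 are met at a scheduled visit.
- For one 20-point fall per affected subject within 12 months, the mean at any one visit moves by 20 × p × w/12. With p = 5% and w = 1 this is 0.08 points; with p = 10% and w = 3 it is 0.5 points.

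**3. Would a worst-value or threshold count be a safe remedy?**

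Consider a count of subjects with a fall of 10 points or more to below 50%, and suppose LVEF never truly changes.

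Assumed: true LVEF normal with mean 60 and SD 6; SD of change between two ECHOs 5, 7 or 10, so error per ECHO is SD/√2; treatment time exponential.

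From the documents:

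- measured baseline at least 40% (inclusion criterion 109);
- Kd median treatment time set to 11 months (48 weeks of carfilzomib in the earlier Kd trial, Protocol 2.5.4) or 18.7 months (median PFS on Kd, Protocol Table 1);
- KdD median = Kd median / 0.6, borrowing the planning hazard ratio: 11/0.6 = 18.3 and 18.7/0.6 = 31.2 months;
- follow-up of 16 to 27 months at the primary analysis (27 minus 11 months' accrual, Protocol 3.5), or 48 months (maximum treatment, SAP 3.1);
- number of ECHOs = whole 6-month periods on treatment within follow-up.

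By simulation, one ECHO gives a false count in 0.6%, 2.4% and 6.2% of subjects at SD 5, 7 and 10. Two ECHOs at SD 7 give 4.5%. Results by arm at SD 7 (excess taken from unrounded values):

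| Follow-up (months) | Kd median (months) | Mean ECHOs Kd / KdD | Falsely counted Kd / KdD | KdD excess (points) |
|---|---|---|---|---|
| 16–27 | 11 | 1.5 / 2.0 | 3.2% / 4.2% | about 1.0 |
| 16–27 | 18.7 | 2.0 / 2.4 | 4.2% / 5.0% | about 0.8 |
| 48 | 11 | 2.1 / 3.3 | 4.1% / 6.1% | about 2.0 |
| 48 | 18.7 | 3.3 / 4.6 | 6.2% / 8.1% | about 2.0 |

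At SD 5 the excess is about 0.2 to 0.3 points by the primary analysis and 0.6 at 48 months. At SD 10 it is about 1.8 to 2.3 and 4.5.

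Compare a real signal at SD 7. Suppose 5% of KdD and 2.5% of Kd subjects have a transient 10-point fall seen at one event ECHO, and that such a subject is counted with probability 33.2%, against 2.4% from noise. The arm difference is (0.05 − 0.025) × (33.2 − 2.4) = 0.8 points, no larger than the artefact.

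**The case against.** The case for leaving 9.7.4 alone is substantial, and most of it stands.

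- **The sentence can be read generously.** The section opens by listing LVEF among the ECHO measures, so descriptive statistics for unscheduled ECHOs could include LVEF, with events only as the denominator. That reading is open, but the SAP does not state it, and its unit would still be events.
- **Scheduled-only wording is not decisive.** A reader might infer that "and vital signs at each scheduled assessment" shuts unscheduled LVEF out of every table. The documents do not support that: the same endpoint bullet covers laboratory values, for which SAP 9.6.3 includes unscheduled results. Where exclusion is meant, as for vital signs in SAP 9.6.4, it is stated. SAP 9.7.4 is silent.
- **The SAP does not depart from the protocol.** Protocol 10.4.4 asks only for descriptive changes from baseline, and the SAP delivers more than that.
- **Cardiac toxicity is not hidden.** A reader might infer that it is. SAP 9.6.2 gives treatment-emergent events by term and grade, events leading to withdrawal of investigational product, and events of interest. Protocol 7.3.4 collects work-up results for selected cardiopulmonary events. What these tables do not give is the measured LVEF.
- **Worst-value reporting is not free.** Step 3 of the working bears this out.

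What remains is narrow: the plan collects LVEF at the event ECHOs without committing to report it per subject.

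**Conclusion.** The point holds as a gap in commitment. SAP 9.7.4 does not undertake to report LVEF, or affected subjects, at unscheduled ECHOs, so the depth of falls that recover between visits or end treatment may go unreported. The stronger statement, that depth and frequency will certainly go unreported, is not supported, because the wording is loose enough to admit LVEF values and sustained falls will show at scheduled visits.

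The size cannot be taken from the documents. The 17% to 50% detection range and the noise excess rest on assumed fall durations, measurement variability and treatment times. The gap itself rests on the SAP's wording alone.

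This is a minor, optional improvement to descriptive safety reporting, with no bearing on alpha, power or any efficacy conclusion.

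**What to change.** In SAP 9.7.4:

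1. Keep the by-visit tables as they are.
2. Change the basis of the unscheduled-ECHO sentence from events to subjects. By arm, on the Safety Analysis Set, give the number and percent of subjects with at least one unscheduled ECHO, with LVEF and change from baseline at that ECHO.
3. Add a by-subject listing of baseline, event and next available LVEF.
4. Add a worst-post-baseline or threshold count only over a common window (for example, ECHOs through month 6 or month 12) or with adjustment for the number of ECHOs, and without a test. The threshold must be fixed in advance; the only LVEF limit in the documents is the 40% entry criterion.
5. Footnote these outputs with both sources of arm imbalance: unequal treatment time, and symptom-driven testing in an open-label trial.

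Items 2 and 3 cost one revised summary and one listing from data already collected, with no new assessments. Item 4 is optional; if it cannot be restricted or adjusted in this way, leave it out.

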9.7.5 Pulmonary Function Test

Pulmonary Function Tests, including Spirometry and DLCO, will be summarized by actual values and changes from baseline values by visit using descriptive statistics for each treatment group.

10. Changes From Protocol-specified Analyses

SAP contains some changes in subgroups from Protocol:

- **Added below subgroups:**
 - **prior Bortezomib or Ixazomib exposure (yes vs no)**
 - **refractory to Bortezomib or Ixazomib (yes vs no)**
 - **prior IMiD exposure (yes vs no)**
 - **refractory to IMiD (yes vs no)**
- **Changed risk groups determined by FISH to risk groups determined by genetic abnormality per IMWG**

11. Literature Citations / References

- Clopper CJ and Pearson ES. The use of confidence or fiducial limits illustrated in the case of the binomial, *Biometrika*. 1934; 26(4):404-413.
- Collett D. *Modelling Survival Data in Medical Research*. 2nd edition. London, UK: Chapman & Hall/CRC; 2003.
- Kalbfleisch, J. D. and Prentice, R. L. *The Statistical Analysis of Failure Time Data*, New York: John Wiley & Sons; 1980
- Klein, J. P. and Moeschberger, M. L. (1997), *Survival Analysis: Techniques for Censored and Truncated Data*, New York: Springer-Verlag.

- 2 = Impute the first day of the month
- 3 = Impute January 1 of the year
- 4 = Impute January 1 of the stop year

Note: If the start date imputation leads to a start date that is after the stop date, then do not impute the start date.

Imputation rules for partial or missing stop dates:

For partial stop date mmyyyy, impute the last day of the month.

For partial stop date yyyy, impute December 31 of the year.

For completely missing stop date, do not impute.

If the stop date imputation leads to a stop date that is after the death date, then impute the stop date as the death date.

If the stop date imputation leads to a stop date that is before the start date, then there is a data error and do not impute the stop date. (ie. set the stop date as missing).

A2. The anti-cancer therapy date will be imputed using the following algorithm:

If the start day of new anti-cancer therapy is missing and month and year are not the same as last dosing date of study treatment, it will be assumed to be the first day of the month. If the start day of new anti-cancer therapy is missing and month and year are same as last dosing date of study treatment, and the patient does not have protocol deviation of using excluded procedure while on study, the start date will be assumed as last dosing date of study treatment plus 1 day. In other situations, do not impute.

Appendix B. Code Fragment

```
CC [REDACTED]  
[REDACTED]  
[REDACTED]  
[REDACTED]  
[REDACTED]  
[REDACTED]  
[REDACTED]  
[REDACTED]  
[REDACTED]  
[REDACTED]  
[REDACTED]
```

Appendix C. Reference Values/Toxicity Grades

Laboratory Values

Safety laboratory values below a distinct limit (eg. detection limit, documented as “< [limit]”) will be substituted by half of the limit and values above a distinct limit (documented as “> [limit]”) will be substituted by the limit itself for all analyses.

A Grade will be assigned to each laboratory based on CTCAE version 4.0 [v4.03: June 14, 2010], as detailed in [Table 5](#). Depending on the toxicity definition, the same result may be assigned to two grading for deviations towards higher or lower values. Values not meeting any of the criteria will be assigned a grade 0.

Table 5. Grading of Select Laboratory Parameters

Laboratory Abnormality [Unit]	Grade 1	Grade 2	Grade 3	Grade 4
Decreased Hemoglobin [g/L]	100 - < LLN	80 - < 100	< 80	not defined
Decreased Lymphocytes [G/L]	0.8 - < LLN	0.5 - < 0.8	0.2 - < 0.5	< 0.2
Decreased Neutrophils [G/L]	1.5 - < LLN	1.0 - < 1.5	0.5 - < 1.0	< 0.5
Decreased Platelets [G/L]	75 - < LLN	50 - < 75	25 - < 50	< 25
Decreased WBC [G/L]	3.0 - < LLN	2.0 - < 3.0	1.0 - < 2.0	< 1.0
Increased AST	> ULN – 3×ULN	> 3×ULN – 5×ULN	> 5×ULN – 20×ULN	> 20×ULN
Increased ALT	> ULN – 3×ULN	> 3×ULN – 5×ULN	> 5×ULN – 20×ULN	> 20×ULN
Increased Total Bilirubin	> ULN – 1.5×ULN	> 1.5×ULN – 3×ULN	> 3×ULN – 10×ULN	> 10×ULN
Increased Corrected Calcium [mmol/L]	> ULN - 2.9	> 2.9 – 3.1	> 3.1 – 3.4	> 3.4
Increased Creatinine	> 1 - 1.5×BL or > ULN - 1.5×ULN	> 1.5 - 3.0×BL or > 1.5 - 3.0×ULN	> 3.0×BL or > 3.0-6.0×ULN	> 6.0×ULN
Increased Potassium [mmol/L]	5.5 - > ULN	> 5.5 – 6.0	> 6.0 – 7.0	> 7.0

Page 1 of 2

Footnotes defined on next page of table

Table 5. Grading of Select Laboratory Parameters

Laboratory Abnormality [Unit]	Grade 1	Grade 2	Grade 3	Grade 4
Increased Sodium [mmol/L]	> ULN – 150	> 150 – 155	> 155 – 160	> 160
Increased Magnesium [mmol/L]	> ULN – 1.23	not defined	> 1.23 – 3.30	> 3.30
Increased Uric Acid [mmol/L]^	> ULN – 0.59 without physiologic consequences	not defined	> ULN – 0.59 with physiologic consequences	> 0.59
Decreased Albumin [g/L]	30 – < LLN	20 – < 30	< 20	not defined
Decreased Corrected Calcium [mmol/L]	2.0 – < LLN	1.75 – < 2.0	1.5 – < 1.75	< 1.5
Decreased Potassium [mmol/L]*	3.0 – < LLN	3.0 – < LLN; symptomatic; intervention indicated	2.5 – < 3.0	< 2.5
Decreased Magnesium [mmol/L]	0.5 – < LLN	0.4 – < 0.5	0.3 – < 0.4	< 0.3
Decreased Phosphorus [mmol/L]	0.8 – < LLN	0.6 – < 0.8	0.3 – < 0.6	< 0.3
Decreased Sodium [mmol/L]	130 – < LLN	not defined	120 – < 130	< 120

Page 2 of 2

BL: baseline value, LLN: Lower limit of normal, ULN: Upper limit of normal

Clinical criteria from CTCAE 4.0 grading were not considered in order to assign grades unless specified otherwise

*: Details will be recorded on Potassium CTC Details CRF for central lab values and Chemistry (Local Lab) CRF for local lab values.

^: Details will be recorded on Uric Acid CTC Details CRF for central lab values and Chemistry (Local Lab) CRF for local lab values.

